6.3.3. Germline *BRCA1* and *BRCA2* Mutational Testing

All patients must lack of deleterious or suspected deleterious germline BRCA mutation to be eligible; this will be assessed via central testing by Myriad unless test have been done previously at Myriad.

Central *BRCA* assessment will require the shipment of one blood sample (9-10 ml) collected in EDTA tubes.

Blood samples for mutational *BRCA* screening analysis must be sent to the central laboratory following shipment instructions in the SMM, once signed the specific ICF for this mutational analysis. Signature of ICF and shipment of blood samples could be performed either simultaneously to the shipment of the tumour samples for methylation analysis or before, in previous lines of treatment, once inclusion/exclusion criteria have been reviewed and the patient is considered a potential candidate to the study (at least the patient must have measurable disease and biopsiable disease).

Results of *BRCA* mutation analysis will be provided to investigator within 10 working days after the day the samples are received in the central laboratory, unless extra-time is needed for justified reasons (e.g. in case of finding a variant of uncertain significance).

The analysis will be performed in Myriad Genetics laboratories Inc. at Salt Lake City (Utah, USA), using the *BRACAnalysis CE test*, which counts with the EU certificate about compliance of the directive 98/79/EC on in vitro diagnostic medical devices.

The gBRCA mutational status result from the Myriad assessment will be provided to the Investigator and will be collected as part of the patient's demography and medical history details.

6.3.4. Other Biomarker Assessments

The following samples will be collected to achieve secondary objectives and exploratory work.

Blood specimens: Blood samples will be collected prior and after treatment to assess germinal methylation status and mRNA levels of *BRCA 1* and *2*. Methylation data will be used to assess correlation of germinal methylation status with outcome data and evaluate correlation between germinal and somatic methylation status. *BRCA* expression results will be correlated with the methylation status and outcome data. Changes of *BRCA* methylation and expression levels during the study and after progression will be explored.

Blood samples will be also retained for exploratory biomarker analyses related to drug response or adverse drug reactions. Genomic, epigenetic, metabolomic and proteomic variation may help to explain some of the variability in response seen among different individuals. Comparing the DNA, RNA, protein, and metabolite patterns of patients who respond well and those who respond poorly to treatment may help to better define the most appropriate group of patients in which to target a given treatment. For example, putative safety biomarkers, drug metabolizing enzyme genes, drug transport protein genes, or genes thought to be related to the mechanism of drug action may be examined. As indicated in table 13 blood samples prior to treatment will be collected for all registered patients, after treatment only from enrolled patients.

Plasma Samples: blood samples collected at time-points showed in table 12 from all enrolled patients will be processed to obtain plasma in study sites. Plasma samples will be collected for exploratory analyses of circulating free DNA or RNA or other biomarkers and their relationship to resistance or sensitivity to treatment with olaparib. Plasma samples may also be analyzed to explore the pharmacodynamic (PD) treatment effects on the expression of specific biomarkers.

Tumour Tissue: FFPE samples from primary and metastatic tumour will be collected as indicated in Table 13 in order to address correlation between primary and metastatic lesions.

Retrospective, exploratory tumour tissue biomarkers, including DNA, RNA and protein analytes, could be analysed to investigate possible associations with resistance/sensitivity to treatment with olaparib. Examples of such biomarkers may include but not limited to somatic *BRCA1/2* mutational status or other genes related to cancer susceptibility and though to be related to the drug mechanism of action. These samples will be instrumental to explore biomarkers of response and biomarkers of primary resistance to olaparib.

The relationship between centrally assessed biomarkers and resistance/sensitivity to treatment with olaparib will be reported in an exploratory fashion.

Blood and tumour samples for secondary and exploratory objectives will be sent to the central pathology laboratory where they will be kept until analysis is performed in analysis laboratories appointed by GEICAM.

7. Data Quality Assurance

To ensure accurate, complete and reliable data, GEICAM will do the following:

- Provide instructional material to the study sites, as appropriate
- Sponsor a start-up training session to instruct the Investigators and study coordinators. This session will give instructions on the protocol, the completion of the eCRFs, and study procedures
- Make periodic visits to the study site to review study progress, Investigator and patient compliance with the clinical trial protocol requirements and any emergent problems.
- Be available for consultation and stay in contact with the study site personnel by mail, telephone, and/or fax
- Review and evaluate eCRF data and use standard computer edits to detect errors in data collection
- Conduct a quality review of the database
- Verify the quality of the data

To ensure the safety of participants in the study and to ensure accurate, complete, and reliable data, the Investigator will keep records of laboratory tests, clinical notes, and patient medical records in the patient files as original source documents for the study. If requested, the Investigator will provide GEICAM, applicable regulatory agencies, and applicable ethical review boards with direct access to original source documents.

7.1. Data Management and Registries File

Data for this study will be recorded via an electronic data capture system using eCRFs. Data will be transcribed by the site from the paper source documents onto the eCRF. In no case the eCRF is to be considered as source data for this trial. The eCRFs must be completed in an electronic Data Base. That electronic Data Base carries out with the regulatory authorities requirements. It is the responsibility of the Investigator to maintain adequate and accurate eCRFs (according to the technology used) designed by GEICAM to record (according to GEICAM instructions) all observations and other data pertinent to the clinical investigation. All eCRFs should be completed in their entirety in a neat, to ensure accurate interpretation of data.

Should a correction be made, the corrected information will be entered in the eCRF overwriting the initial information. An audit trail allows identifying the modification.

Data are available within the system to GEICAM as soon as they are entered in the eCRF.

The computerized handling of the data by GEICAM when available in the eCRF may generate additional requests to which the Investigator is obliged to respond by confirming or modifying the data questioned. The requests with their responses will be managed through the eCRF.

8. Sample Size and Statistical Methods

8.1. Determination of Sample Size

8.1.1. Sample Size Determination

We have set the null hypothesis (H0) that ORR will be 30% (ORR achieved by TN patients treated with gemcitabine plus carboplatin¹) versus the alternative hypothesis (H1) that ORR will be 54% (ORR showed by TN *BRCA* mutated patients treated with olaparib²). Using an optimal two-stage Simon model and considering an alpha error of 0.05 and a statistical power of 80%, it will be required to include 31 evaluable patients. Twelve evaluable patients will be enrolled in the first stage, and if at least 4 patients of them have response, additional patients will be recruited to get a total of 31 evaluable patients. Assuming a 10% dropout rate, the total number of patients to be enrolled is 34. Considering, these data the number of responders needed at the end of stage 2 to reject the null hypothesis is at least 14 responders.

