- 19. *Patients considered a poor medical risk due to a serious, uncontrolled medical disorder, non-malignant systemic disease or active, uncontrolled infection or laboratory abnormality that may increase the risk associated with study participation or may interfere with the interpretation of study results and, in the judgment of the investigator, would make the patient inappropriate for entry into this study. Examples include, but are not limited to, uncontrolled ventricular arrhythmia, recent (within 3 months) myocardial infarction, uncontrolled major seizure disorder, unstable spinal cord compression, superior vena cava syndrome, severe hepatic impairment (according to Child-Pugh classification), an extensive interstitial bilateral lung disease on High Resolution Computed Tomography (HRCT) or any psychiatric disorder that prohibits obtaining informed consent.
- 20. *Previous allogenic bone marrow transplant or double umbilical cord blood transplantation (dUCBT).
- 21. *Whole blood transfusions in the last 120 days prior to entry to the study (packed red blood cells and platelet transfusions are acceptable, for timing refer to inclusion criteria n° 10).

Justification of Sample size determination:

We have set the null hypothesis (H0) that ORR will be 30% (ORR achieved by TN patients treated with gemcitabine plus carboplatin¹) versus the alternative hypothesis (H1) that ORR will be 54% (ORR showed by TN BRCA mutated patients treated with olaparib²). Using an optimal two-stage Simon model and considering an alpha error of 0.05 and a statistical power of 80%, it will be required to include 31 evaluable patients. Twelve evaluable patients will be analysed in the first stage, and if at least 4 patients of them have tumour response, additional patients will be recruited to get a total of 31 evaluable patients. Assuming a 10% dropout rate, the total number of patients to be enrolled is 34. Considering, these data the number of responders needed at the end of stage 2 to reject the null hypothesis is at least 14 responders.

Statistical Analyses:**➤ Demographics and Baseline Characteristics**

Standard descriptive statistics, such as the mean, median, range and proportion, will be used to summarize the patient sample and to estimate parameters of interest.

➤ Safety Analyses

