Exploratory subgroup analysis may be performed if deemed appropriate.

8.2.10. *Interim Analysis*

There is no planned any interim analysis.

The optimal two stage Simon Model is carried out in two steps. The purposes of the step 1 analysis is to allow early stopping of the study for futility.

Following the two-stage Simon design, it will be reviewed whether 4 of the first 12 evaluable patients show tumour response according to RECIST v.1.1, and if this occurs, additional patients will be included to get a total of 34 patients.. If 3 or less than 3 patients of the first 12 evaluable patients show an OR, recruitment will be stopped.

8.2.11. *Criteria for End of Study*

This study will be considered complete following the data cut-off date and datalock for the final analysis. The data cut-off date for the final analysis will occur after all enrolled patients have died or withdraw of the informed consent or there is sufficient data to achieve the primary and secondary objectives, whatever occurs first. It is estimated that the final analysis could be performed approximately 30 months after the enrolment of the first patient because, considering a median OS of 12 months, it is estimated that more than 50% of death events will have occurred at that time and overall survival analysis could be performed. If further data are collected that are not included as part of the final locked

database, the post-lock data will eventually be combined with the locked database and stored in a data library separate from the locked database.

Performing exploratory objectives will be independent of the date of the end of the study.

9. Informed Consent, Confidentiality, Responsibility Insurance and Regulatory Considerations

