### 3.1 Sample Size

We have set the null hypothesis (H0) that ORR will be 30% (ORR achieved by TN patients treated with gemcitabine plus carboplatini) versus the alternative hypothesis (H1) that ORR will be 54% (ORR showed by TN *BRCA* mutated patients treated with olaparibii). Using an optimal two-stage Simon model and considering an alpha error of 0.05 and a statistical power of 80%, it will be required to include 31 evaluable patients. Twelve evaluable patients will be enrolled in the first

stage, and if at least 4 patients of them have response, additional patients will be recruited to get a total of 31 evaluable patients. Assuming a 10% dropout rate, the total number of patients to be enrolled is 34. Considering, these data the number of responders needed at the end of stage 2 to reject the null hypothesis is at least 14 responders.

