## 8. INTERIM ANALYSIS

There is no planned any interim analysis.

The optimal two stage Simon Model is carried out in two steps. The purposes of the step 1 analysis are to allow early stopping of the study for futility.

Following the two-stage Simon design, it will be reviewed whether if at least 4 of the first 12 evaluable patients show tumour response according to RECIST version 1.1, and if this occurs,

additional patients will be included to get a total of 34 patients. If 3 or less patients of the first 12 evaluable patients show an OR, recruitment will be stopped.

In case of recruitment is stopped after the step 1, it will be reviewed the feasibility and interest of performing some of the described secondary and exploratory analysis based on the available number of patients and samples.

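### The stage-1 boundary is one responder too low: the optimal Simon design for the stated inputs continues only at 5 or more of 12, not 4 or more

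*Protocol*

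**What the plan says.** Protocol 8.1.1 sets the hypotheses as "We have set the null hypothesis (H0) that ORR will be 30" per cent against "the alternative hypothesis (H1) that ORR will be 54" per cent. It describes the method as "Using an optimal two-stage Simon model and considering an alpha error of 0.05 and a statistical power of 80" per cent. From these it takes 31 evaluable patients, 12 of them in stage 1, and rejection of the null at 14 or more responders.

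The stage-1 rule is that "if at least 4 patients of them have response, additional patients will be recruited to get a total of 31 evaluable patients". Protocol 8.2.10 gives the other side of the same boundary: "If 3 or less than 3 patients of the first 12 evaluable patients show an OR, recruitment will be stopped".

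The rule is the same throughout. The synopsis sample-size paragraph has "if at least 4 patients of them have tumour response", and the synopsis design paragraph and Protocol 3.1.1 also use 4 of 12. SAP 3.1 repeats "if at least 4 patients of them have response, additional patients will be recruited to get a" total of 31, and SAP 8 states "If 3 or less patients of the first 12 evaluable patients show an OR, recruitment will be stopped". Neither document mentions a boundary of 5, gives a reason for a looser one, or reports the exact alpha, power or early-stopping probability of the rule.

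**The concern.** In Simon's notation a design is written r1/n1, r/n. The trial stops if r1 or fewer of n1 respond, and the null is rejected if more than r of n respond. A tabulated r1 of 4 therefore means stop at 4 and continue at 5. The plan's final rule, at least 14 of 31, corresponds to r = 13 read correctly. Its stage-1 rule, continue at 4, corresponds to r1 = 3.

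If the optimal design has r1 = 4, the rule in the plan is not the design that the plan names, and its stated alpha, power and optimality do not belong to it. Step 1 exists only to allow stopping for futility. No other interim analysis is planned, and SAP 8.2 marks a monitoring committee as not applicable, so this is the only numerical futility rule in the trial.

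The boundary may well be tested. Protocol 1.3 reports minimal efficacy of PARP inhibitors in sporadic breast cancer. The 54% target comes from patients with BRCA mutations, whereas this trial excludes germline carriers.

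**Working it through.** **Inputs (Protocol 8.1.1).** p0 = 0.30, p1 = 0.54, alpha = 0.05, power = 0.80, n1 = 12, n = 31, reject at 14 or more (r = 13). As written, r1 = 3.

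**Formulas.** Let X1 ~ Bin(12, p) and X2 ~ Bin(19, p), since 31 − 12 = 19.

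- Probability of early stopping: PET(p) = P(X1 ≤ r1)
- Probability of rejecting: R(p) = Σ over x > r1 of P(X1 = x) × P(X2 ≥ 14 − x). Alpha = R(0.30); power = R(0.54).
- Expected sample size: EN = 12 + (1 − PET) × 19

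**Step 1: reproduce the plan's design.** All two-stage designs up to n = 50 were searched with exact binomial probabilities, keeping those with alpha ≤ 0.05 (one-sided) and power ≥ 0.80 and minimising EN under the null. The optimum is 4/12, 13/31. This matches the plan's 12, 31 and 14, but its stage-1 rule is stop at 4 or fewer, continue at 5 or more.

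**Step 2: compare the two boundaries.** The stage-1 probabilities under the null are P(X1 ≤ 3) = 0.4925 and P(X1 = 4) = 0.2311, so P(X1 ≤ 4) = 0.7237.

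| | As written (continue at ≥ 4) | Optimal (continue at ≥ 5) |
|---|---|---|
| Early stopping, ORR 30% | 0.4925 | 0.7237 |
| Continuing, ORR 30% | 0.507 | 0.276 |
| Expected N, ORR 30% | 12 + 0.5075 × 19 = 21.64 | 12 + 0.2763 × 19 = 17.25 |
| Exact alpha | 0.0503 | 0.0428 |
| Early stopping, ORR 54% | 0.0415 | 0.1258 |
| Exact power | 0.8612 | 0.8073 |

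The relative loss of early stopping under the null is 1 − 0.4925/0.7237 = 32%. The increase in expected N is 21.64 − 17.25 = 4.4 patients.

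**Step 3: check that one outcome accounts for the difference.** The rules disagree only at exactly 4 of 12. From there, success needs at least 10 of the remaining 19.

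- ORR 30%: 0.2311 × P(X2 ≥ 10) = 0.2311 × 0.0326 = 0.0075, and 0.0428 + 0.0075 = 0.0503.
- ORR 54%: 0.0844 × 0.6383 = 0.0539, and 0.8073 + 0.0539 = 0.8612.

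**Step 4: can another final cut-off rescue the written boundary?** No. With r1 = 3, n1 = 12 and n = 31, a cut-off of 14 gives alpha 0.0503. A cut-off of 15 gives alpha 0.0231 but power 0.780. No cut-off meets both stated limits.

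**Step 5: could the rule come from other inputs?** None of the variants tried gives continuation at 4 of 12 with a total of 31.

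| Variant | Design |
|---|---|
| Minimax, same inputs | 4/13, 12/28 |
| Optimal, one-sided 0.025 | 3/10, 16/37 |
| Optimal, power 0.90 | 6/18, 17/42 |
| Optimal, p1 = 0.55 | 3/9, 14/35 |
| Optimal, alpha 0.10 | 2/8, 8/20 |

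**The case against.** Nobody can dispute the search result. The case on the other side is about weight and cause.

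- **Alpha.** The excess is 0.0003, and 0.0503 rounds to the stated 0.05. This stands: the alpha breach is real but has no practical importance.
- **The written rule has advantages.** It has more power (86% against 81%) and wrongly stops an active drug less often (4.1% against 12.6% at ORR 54%). After exactly 4 of 12, a 30% drug goes on to a false positive only 3.3% of the time. This also stands. The cost is mainly extra patients treated with an inactive drug, not misleading positive results.
- **A deliberate choice.** The rule is consistent across both documents, so a lenient boundary may have been intended. That cannot be excluded, and a misread r1 is an inference. However, the other three design numbers all match the optimal design, and the plan gives no reason for departing from it on the fourth. If the choice was deliberate, the word optimal and the unstated operating characteristics are still wrong.
- **Other ways to stop.** Protocol 4.4.3 lets the sponsor discontinue on new information about effectiveness. That is a general power, not a numerical futility rule.
- **Dependence on 31.** The figures assume exactly 31 evaluable patients, while Protocol 3.1.1 and 8.2.10 and SAP 8 speak of reaching 34. If all 34 were evaluable and the cut-off stayed at 14, alpha would be 0.098 as written and 0.077 with the boundary at 5. This is a fair condition on the figures, but it does not affect which stage-1 boundary belongs to the 31-patient design.

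**Conclusion.** The point holds and must be fixed. The stage-1 decision rule contradicts the design that the plan says it uses. What matters is the weakened futility stop: a drug with a true ORR of 30% goes on to full enrolment 51% of the time, against 28% under the optimal design, at a cost of 4.4 more patients expected. Exactly 4 of 12 responders has probability 23% under the null, and on that result the written rule continues where the optimal design stops.

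The figures rest on the stated response rates, a one-sided alpha of 0.05 (the only level tried that reproduces 31 patients), exactly 31 evaluable patients at the end, and a trial stopped at stage 1 counting as a failure to reject. They also assume that the 12 stage-1 patients are the first 12 of the final 31. Protocol 8.2.5 applies an 80% dose requirement at step 1 only, so the two sets may differ.

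**What to change.** Choose one of two routes and apply it in the protocol synopsis (both places), Protocol 3.1.1, 8.1.1 and 8.2.10, and SAP 3.1 and 8.

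1. **Adopt the optimal boundary.** Continue if at least 5 of the first 12 evaluable patients respond; stop if 4 or fewer do. State the exact operating characteristics: alpha 0.043, power 80.7%, early stopping under the null 72%, expected N under the null 17.3.
2. **Keep 4 or more.** Remove the word optimal, say that the boundary is deliberately lenient and why, and state alpha 0.0503, power 86.1%, early stopping under the null 49% and expected N under the null 21.6.

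Under either route, say that these figures apply to a final analysis of exactly 31 evaluable patients.

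The cost is one wording amendment to the protocol and SAP, with no increase in sample size. Route 1 lowers expected enrolment under the null by about 4 patients. In exchange, power falls from an unstated 86% to about the stated 80%, and the chance of stopping an active drug early rises from 4.1% to 12.6%. The change should be made before stage-1 responses are known, because a boundary moved afterwards would not be credible.

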8.2. Statistical and Analytical Plans

8.2.1. General Considerations

Statistical analysis of this study will be the responsibility of GEICAM. The interpretation of study results will be the responsibility of the Chief Investigator of the study.

Detailed methodology for summary and statistical analyses of the data collected in this study will be documented in a Statistical Analysis Plan (SAP), which will be dated and maintained by GEICAM. This document may modify the plans outlined in the protocol; however, any major modifications of the primary endpoint definition and/or its analysis will also be reflected in a protocol amendment.

All analysis will be performed using the SAS Enterprise Guide 5.1 version.

8.2.1. Patient Populations

Intent to treat population (ITT): The ITT population will include all patients who are enrolled in the study.

Efficacy population: a subset of the ITT population that have received at least one dose of study medication and has performed at least one tumour response assessment according to RECIST v.1.1 (unless a progression, death or unacceptable toxicity is seen before the first tumour response assessment) and without major protocol deviations according to the protocol deviation manual.

The **efficacy** population will be the primary population for the efficacy analysis.

It will be performed a sensitivity analysis using the ITT population.

Safety population: will include all patients enrolled in the study who received at least one dose of treatment. This population is for the safety analysis.

Population for Biomarker Analysis: a subset of enrolled patients with evaluable blood and/or tumour samples required for achievement of the secondary and exploratory objectives of the study.

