4.4. Discontinuations

4.4.1. Discontinuation of Study Drugs/Medications

The criteria for enrolment must be followed explicitly. If a patient who does not meet enrolment criteria is inadvertently enrolled, that patient should be discontinued from the study drugs/medications, but can be allowed to continue in the study in order to provide the follow-up data needed for the analysis of the entire population. An exception may be granted if the patient, in the opinion of the Investigator, is having benefit from the study drugs/medications. In these rare cases, the investigator must obtain documented approval from GEICAM to allow the patient to continue to receive the study drugs/medications.

Patients can be discontinued from the study therapy in the following circumstances:

- Patient's own request. The patient is at any time free to discontinue treatment, without prejudice to further treatment.
- Unacceptable toxicity as defined in the protocol.
- Any clinical adverse event (AE), laboratory abnormality or inter-current illness which, in the opinion of the investigator, indicates that continued participation in the study is not in the best interest of the patient.
- Bone marrow findings consistent with myelodysplastic syndrome (MDS)/acute myeloid leukaemia (AML)
- Pregnancy:
 - ✓ Instruct to contact the investigator or study staff immediately if they suspect they might be pregnant.
 - ✓ The investigator must immediately notify GEICAM if a study patient becomes pregnant.
- Tumour progression as defined in the protocol.
- Severe non-compliance with the study protocol by the patient
- Loss of ability to freely provide consent through imprisonment or involuntarily incarceration for treatment of either a psychiatric or physical (e.g. infectious disease) illness.
- Physician's decision, including need of other anti-cancer therapy, not specified in the protocol.
- Termination of the study by GEICAM.

All permanent treatment discontinuation should be recorded by the Investigator in the eCRF when considered as confirmed.

It is important to discriminate between discontinuation of study treatment only and withdrawal from study (study treatment and follow up).

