8.2.6.1. Analyses of Primary Endpoint

The primary endpoint is ORR

Objective Response Rate (ORR): A patient will be considered to have achieved an OR if the patient has a sustained complete response (CR) or partial response (PR) according to RECIST v.1.1 definitions. Otherwise, the patient will be considered as non-responders in the ORR analysis. ORR will be estimated by dividing the number of patients with objective response (CR or PR) by the Efficacy population ("response rate").

$$\text{Objective Response Rate} = \frac{\text{Number of CRs + PRs}}{\text{Efficacy population}}$$

The ORR will be reported, including a 95% confidence interval.

These analyses will be conducted at a two-sided 0.05 level of significance.

The number of responders needed at the end of stage 2 to reject the null hypothesis is at least 14 responders.

Additional sensitivity analyses will be outlined in the SAP. For the analysis in the ITT population, patients with inadequate data for tumour assessment (e.g., no baseline assessment or no follow-up assessments) will be considered as non-responders in the OR rate analysis.

In addition, the best objective response for each patient will be summarized.

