### **4.2 Efficacy population**

A subset of the ITT population that have received at least one dose of study medication and has performed at least one tumour response assessment according to RECIST version 1.1 (unless PD, death or unacceptable toxicity is observed before the first tumour response assessment) and without major protocol deviations according to the protocol deviation manual.

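### An undefined toxicity waiver allows a treated, never-scanned patient to be left out of the primary ORR denominator at discretion; the bias is upward, but probably involves 0 to 2 patients

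*Protocol*

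**What the plan says.** The Efficacy population is the primary population for ORR, and ITT is the sensitivity analysis (Protocol 8.2.1, Patient Populations, and 8.2.6.1; SAP 9.2 and 9.2.1.1). Membership needs a dose of olaparib, a RECIST 1.1 response assessment and no major deviation. The assessment is waived in three situations: "unless a progression, death or unacceptable toxicity is seen before the first tumour response assessment" in the protocol, and "unless PD, death or unacceptable toxicity is observed before the first tumour response assessment" in SAP 4.2.

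Protocol 4.4.1 lists as a reason for stopping "Unacceptable toxicity as defined in the protocol", and SAP 4.5.1 repeats it. No section of the protocol gives that definition. Sections 5.4 to 5.4.2 contain rules for interrupting, reducing and stopping olaparib, but none is tied to the term.

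The next item in the same list is a separate reason: "Any clinical adverse event (AE), laboratory abnormality or inter-current illness which, in the opinion of the investigator", makes continued participation contrary to the patient's interest. The waiver does not mention it.

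Two other provisions bear on the same patients. Protocol 3.1 and SAP section 3 make a patient who stops for global deterioration without any assessment not evaluable for response rate. Protocol 8.2.5 requires the twelve step 1 patients to have received at least 80% of the planned dose.

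**The concern.** Take two dosed patients who both stop for an adverse event before the first scan and are never scanned. If one event is judged unacceptable toxicity, that patient is a non-responder in the primary analysis. If the other is judged an adverse event that makes continuing unwise, that patient can leave the denominator. Nothing written separates the two judgements, and the population definitions do not say when the judgement is made. The trial is single-arm, and response is derived from local assessment (Protocol 8.2.6).

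The direction is fixed: a patient without a scan cannot add a response, so leaving her out never lowers ORR. The design also counts evaluable patients (12, then 31), so a patient left out is replaced by one who was assessed. The step 1 count and the final rule of at least 14 responders are both exposed.

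**Working it through.** **Inputs.** Protocol 8.1.1: null ORR 0.30, alternative 0.54, alpha 0.05, power 80%; continue with at least 4 responders in 12; reject with at least 14 in 31; 34 enrolled. Protocol 1.4.5.2 (tablet pooled dataset): 50 of 759 patients stopped for an adverse event. Attachment 1: scans every 8 weeks (± 1 week) from the start of treatment. Protocol 3.2: post-treatment visit 30 (± 7) days after finishing treatment.

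**Reproducing the design.** An exact search for the Simon optimal design at one-sided 0.05 and 80% power gives 12 patients in stage 1, 31 in all and rejection at 14 or more (alpha 0.0428, power 0.807). The 31 and the 14 therefore reproduce. That design continues with at least 5 of 12, whereas the documents continue with at least 4. For the printed rule,

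P(pass) = Σ (x = 4 to 12) P(X1 = x; 12, p) × P(X2 ≥ 14 − x; 19, p),

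which is 0.0503 at p = 0.30 and 0.861 at p = 0.54. The stage 1 difference is a separate matter; here it only sets the baseline at 0.050. These are one-sided probabilities. Protocol 8.2.6.1 says "These analyses will be conducted at a two-sided 0.05 level of significance", but at one-sided 0.025 the optimal total is 37, not 31.

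**How many patients.** 50/759 = 6.6%, and 0.066 × 34 = 2.2 adverse-event stops over the whole treatment period. The share before week 8 is not given. I assume k = 0 to 2 patients left out. The enrolment allowance, 34 − 31 = 3, is an outer limit.

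**When a scan is missed.** The first scan window is day 49 to 63. A patient stopping on day d has the post-treatment visit on day d + 23 to d + 37, and new therapy must wait for it.
- Stop on day 35: visit on day 58 to 72. The scan window opens first, so by default she is scanned.
- Visit on its nominal day, d + 30: it precedes day 49 if d is below 19. New therapy could then start before the scan window opens.
- At any d, Protocol 3.2 lets the visit be brought forward when new therapy cannot wait.

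Once new therapy starts, Attachment 1 (note r) no longer schedules a scan. That note counts from the last assessment, here the baseline scan, so the scan may fall due earlier than assumed, which narrows the gap.

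**Effect on the decision rule.** Let the ORR in all 31 + k treated patients be 0.30, with the k unscanned patients left out and 31 others evaluable. The rate among those 31 is p = 0.30 × (31 + k)/31.

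| k | p among the 31 | P(pass) | 14 responders over all treated |
|---|---|---|---|
| 0 | 0.300 | 0.050 | 14/31 = 45.2% |
| 1 | 0.310 | 0.064 | 14/32 = 43.8% |
| 2 | 0.319 | 0.081 | 14/33 = 42.4% |
| 3 | 0.329 | 0.100 | 14/34 = 41.2% |

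**A milder illustration.** Suppose, purely as an assumption, that half of the 2.2 stops come before week 8, half of those are never scanned, and half of those are not judged unacceptable toxicity. Then k = 2.2 × 0.5 × 0.5 × 0.5 = 0.28, and linear interpolation gives 0.050 + 0.28 × (0.064 − 0.050) = 0.054.

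**The case against.** The strongest reply is that the plan already limits the damage. Scans are tied to the calendar and continue after treatment stops unless progression is confirmed or new therapy has begun. New therapy normally follows the post-treatment visit. The ITT analysis scores patients without follow-up assessment as non-responders, and ORR is reported in both populations, so any gap would be visible. In the study design and duration sections (Protocol 3.1 and 3.2), unacceptable toxicity is the only toxicity reason for ending treatment, so an ordinary reading could cover every adverse-event stop.

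Most of this stands, and it is why the likely number is small. It does not remove the point. ITT is not the primary analysis. The broad reading is available, but Protocol 4.4.1 lists adverse-event stops separately, so a narrower one is available too.

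Three stronger readings are tempting, and the documents do not support them:

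- A reader might infer that nearly all early toxicity stops are excluded, by equating the term with the forced stops in Protocol 5.4 (intolerance after two reductions, or no blood-count recovery after four weeks). Nothing makes that link, and 5.4.2 also allows permanent discontinuation when toxicity recurs on re-challenge.
- A reader might infer that the discontinuation code in the eCRF decides inclusion. The waiver speaks of toxicity being seen or observed and names no eCRF field.
- A reader might infer that any adverse-event stop before week 8 leaves the denominator. Only a patient with no assessment at all, and without progression or death before the first scan, is at risk.

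**Conclusion.** The point holds as a discretionary gap in the primary denominator, not as a certain exclusion. A term that decides membership is said to be defined and is not, and a neighbouring stopping reason falls outside the waiver. The likely number is 0 to 2 patients and nearer 0, because 6.6% covers the whole treatment period and several conditions must coincide. One patient left out would take the chance of a false success from 0.050 to 0.064, and two to 0.081. These figures assume an ORR of 30% in all treated patients, full replacement to 31 evaluable, and a k that the documents do not supply. The baseline under the printed rule is already at 0.05, so even one such patient takes it above the nominal level. The matter should be corrected before lock, but it does not undermine the trial.

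**What to change.** In Protocol 8.2.1 (Patient Populations) and SAP 4.2, replace the unacceptable-toxicity element of the waiver with: *permanent discontinuation of olaparib for any adverse event, laboratory abnormality or intolerance, whatever discontinuation reason is recorded*. Add that these patients count as non-responders in the step 1 and final ORR if they have no post-baseline tumour assessment, and that the observed response is used if they are scanned later.

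Three passages need reconciling with this:
- the 80% dose condition for step 1 in Protocol 8.2.5, which could remove the same patients from the first twelve;
- the not-evaluable rule in Protocol 3.1 and SAP section 3;
- the pointer to a protocol definition in Protocol 4.4.1 and SAP 4.5.1, which should be deleted or directed to a real definition.

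No new data are needed, since discontinuations and the action taken on olaparib for each adverse event are already recorded. The cost is a possibly slightly lower ORR and a protocol amendment. A major change to the primary analysis must be reflected in an amendment (Protocol 8.2.1, General Considerations), and a substantial amendment needs authorisation from the ethics committee and/or the competent authority (Protocol 10.3).
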